RPC-IPAA surgery, the standard curative surgical procedure for UC. Further, incorrect diagnosis and treatment carry potential morbidity from inappropriate and unnecessary surgery and costs. The success outcomes of RPC-IPAA surgery and convalescence depend on correct diagnosis. To address IBD diagnosis ambiguity and delays in IBD clinical settings, investigators developed a proteomic signature to discriminate between UC and CC patients that also will predict the outcome of IC patients for their eventual progress to either UC or CC. Our published data has shown robust evidence supporting presence of human alpha-defensin 5 (DEFA5) in areas of the colon mucosa with aberrant expression of apparent Paneth cell-like cells (PCLCs) or crypt cell-like cells (CCLCs), which identifies an area of colonic ileal metaplasia, consistent with the diagnosis of CC. DEFA5 bioassay discriminated CC and UC in a cohort of all IC patients with accuracy. A fit logistic model with group CC and UC as the outcome and the DEFA5 as independent variable differentiator with a positive predictive value of 96%. These findings were obtained solely from colectomy specimens for both the discovery and validation analyses. Investigators believe that use of endoscopy biopsies would be indifferent, which is the purpose of this prospective patient centered clinical study. Investigators propose to demonstrate that UC and CC, the two unsolved medical subtypes of pathology with no drugs for a cure, can accurately be distinguished molecularly by examining CCLCs-secreted DEFA5 in colonic endoscopy biopsies instantly. Our proposal is highly innovative, as it highlights the robustness of DEFA5 and its clinical relevance to IBD is both in science and the anticipated impact, as investigators seek to better understand difficulty to determine ‘subtypes’ and translate that to improve diagnosis, treatment, clinical outcomes, and quality of life for patients and the realm of clinical care. DEFA5 immunoreactivity in colonic endoscopy biopsies could be a rapid potential diagnostic signature to resolve IC into authentic UC and CC with a first clinic endoscopy biopsy. IC is likely to be eliminated for good.

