to this proposal as an established sampling error by endoscopic biopsy making it does not interfere with results and apropos of this project that each biopsy has complement CCLCs with co-localized DEFA5 clearly restricted in areas of the mucosa with aberrant CCLCs identifies a ubiquitously colonic ileal metaplasia that is consistent with the diagnosis of authentic CC. If successful, widespread use of this approach would not only revolutionize provide accurate diagnoses and the correct treatment regimens for IBD patients, but also it will improve health outcomes and patient quality of life, while reducing medical complications and/or unnecessary drugs, surgeries, & costs.

Conditions

Conditions: Inflammatory Bowel Diseases
 Ulcerative Colitis
 Crohn's Colitis
 Indeterminate Colitis

Keywords: Inflammatory bowel disease
 Crohn's colitis
 Ulcerative colitis
 Indeterminate colitis
 DEFA5
 Molecular diagnostics
 Colonic biopsies
 Colonic ileal metaplasia

Study Design

Study Type: Observational
 Observational Study Model: Cohort

Time Perspective: Cross-Sectional

Biospecimen Retention: Samples With DNA

Biospecimen Description: The research outlined is consistent with the Non-human Welfare Act Criteria because investigators receive de-identified specimens and data from an IRB approved repository, and investigators do not have access to the link by which investigators may re-identify the specimens and data with their source. The research involves the use of human tissue acquired previously using the third-party good faith broker mechanism. Since all identifiers are striped, the tissue samples are considered non-human subjects. Each specimen is assigned a unique barcode identifier to maintain the patient's confidentiality. In no case is the patient's name ever revealed to the users. All information accompanying the specimen(s) uses the bar code identifier.

Enrollment: 230 [Anticipated]

Number of Groups/Cohorts: 5

Groups and Interventions

Groups/Cohorts	Interventions
Crohn's colitis Correlate patient longitudinal study of clinical data and their biopsy data. Investigators will determine DEFA5 levels from endoscopy biopsies from known authentic CC patients.	Diagnostic Test: Diagnostic Test The challenge is the discrimination of IBD into the subtypes with accuracy because it affects surgical care of patients. Investigators have developed a signature discriminator between UC&CC that also predicts the outcome of IC patients into

Groups/Cohorts	Interventions

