Ileum Positive control	Diagnostic Test: Diagnostic Test The challenge is the discrimination of IBD into the subtypes with accuracy because it affects surgical care of patients. Investigators have developed a signature discriminator between UC&CC that also predicts the outcome of IC patients into authentic UC/CC. This is a bioassay that is specific, sensitive, linear, affordable, minimal risk, non-invasive and constitutes an inexpensive, simple to use, point-of-care test format. Our published data have shown robust evidence supporting presence of DEFA5 in the colon crypt mucosa with aberrant expression of apparent crypt-cell-like cells (CCLCs) in areas identified with ectopic colon ileal metaplasia consistent with CC. Investigators propose to validate that UC/CC, the two unsolved medical sub-types of pathology can accurately be distinguished among IC patients by examining CCLCs secreted DEFA5 levels in endoscopy biopsies instantly. Diagnostics relies on the expression/localization/activation of DEFA5 and the ectopic CCLCs in the mucosal crypt of CC patients.

Outcome Measures

Primary Outcome Measure:

1. Assesse investigator's two newly developed anti-DEFA5 monoclonal antibodies for immunohistochemistry and sandwich ELISAs, and determines the most effective one or both for bioassay kit for IBD diagnostics.
 [Time Frame: Six months]

Secondary Outcome Measure:

2. Assess expression of DEFA5 biomarker in colonic biopsies from known patients with the diagnosis of IBD i.e., UC, CC, IC, and none-IBD i.e., diverticulitis, diverticulosis, & ileum as positive control, this will differentiate UC vs. CC and IC into authentic UC and CC.
 [Time Frame: 12 months]

Eligibility

Study Population: A sample size of 230 subjects is sufficient to detect a clinically significant difference of 19% between the PPVs of CC and UC using a one-tailed test of proportions between the two groups with 80% statistical power and a 5% level of significance. This 19% difference represents 80% probability that subjects in the CC group with a positive screening test truly have the disease and 77% PPV for subjects in UC group. Investigators will add non-IBD samples, 46 in the DV arm and 46 in CP arm to strengthen the results.

Sampling Method: Probability Sample

Minimum Age:

Maximum Age:

Sex: All

Gender Based: No

Accepts Healthy Volunteers: Yes

Criteria: Inclusion Criteria:

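### The sample-size statement defines a 19% difference in PPV as 80% versus 77%, which is 3 points, and the claimed 80% power does not follow from those rates

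*Protocol*

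**What the plan says.** The protocol's sample-size justification is in Eligibility, Study Population. It opens: "A sample size of 230 subjects is sufficient to detect a clinically significant difference of 19% between the PPVs of CC and UC". The test is a one-tailed comparison of two proportions with 80% power at the 5% level.

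The next sentence defines the difference: "This 19% difference represents 80% probability that subjects in the CC group with a positive screening test truly have the disease and 77% PPV" in the UC group.

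The paragraph ends: "Investigators will add non-IBD samples, 46 in the DV arm and 46 in CP arm to strengthen the results". Study Design gives the same total, 230, as the anticipated enrollment, spread over five cohorts: CC, UC, indeterminate colitis (IC), diverticulitis and ileum.

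The only other PPV in the document is the 96% reported in the Brief Summary from the investigators' published work. Of that work the protocol says: "These findings were obtained solely from colectomy specimens for both the discovery and validation analyses".

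**The concern.** The second sentence is meant to define the first, but 80% and 77% are 3 points apart, so the two sentences cannot both be right. The required sample size varies roughly with the inverse square of the difference, so the gap between 3 and 19 points decides whether 230 is ample or far too small.

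This paragraph is the only support in the protocol for calling 230 sufficient. If 80% and 77% are the real planning values, the power claim is badly wrong. If a 19-point gap was meant, the power depends on which pair of rates and which group sizes were intended, and the protocol gives neither. A PPV is also calculated only among test-positive subjects, so the number entering the test is smaller than the number enrolled.

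**Working it through.** **Inputs from the protocol.** PPV 80% (CC) and 77% (UC); stated difference 19%; one-sided α = 0.05; power 80%; N = 230; five cohorts; 46 + 46 = 92 non-IBD samples.

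**Assumed.** Equal CC and UC groups. Their size is not given, so three values are used:
- 46 per group: 230/5
- 69 per group: (230 − 92)/2
- 115 per group: 230/2

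Only 46 leaves room for all five cohorts inside 230. The values 69 and 115 leave no separate IC cohort. If the 92 are extra and CC, UC and IC share the 230, the figure is about 77 (230/3).

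**Step 1: the difference.**
- Absolute: 80 − 77 = 3 points.
- Relative: 3/77 = 3.9%.
- Odds ratio: (0.80/0.20)/(0.77/0.23) = 1.195.

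Only the odds ratio comes near 19%. It is not a difference between PPVs or the quantity in a test of proportions, and it leaves the rates, and so the power, unchanged.

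**Step 2: the plan's 80% power, from its printed rates.** With p̄ = (p₁ + p₂)/2, the pooled-variance formula is

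power = Φ{ [ |p₁ − p₂|√n − 1.645√(2p̄(1 − p̄)) ] / √(p₁(1 − p₁) + p₂(1 − p₂)) }

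For 0.80 and 0.77 the two square-root terms in the rates are 0.5810 and 0.5806. At n = 46: (0.03 × 6.782 − 1.645 × 0.5810)/0.5806 = −1.30, and Φ(−1.30) is about 9.8%.

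The n per group for 80% power is (1.645 × 0.5810 + 0.842 × 0.5806)² / 0.03² ≈ 2,318, or 4,636 in total.

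The stated 80% is not reproduced. Even 230 per group gives only 19.4%. Two-sided power is lower still, and an unpooled variance changes nothing material.

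**Step 3: pairs that do differ by 19 points and keep one printed rate.** Entries are one-sided power by pooled z, with Fisher's exact test in parentheses.

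| PPVs | 46 per group | 69 per group | 115 per group | n per group for 80% (pooled z) |
|---|---|---|---|---|
| 80% vs 77% (as printed) | 9.8% (6.1%) | 11.2% (7.6%) | 13.7% (10.5%) | 2,318 |
| 96% vs 77% | 85.6% (81.3%) | 95.4% (94.9%) | 99.6% (99.7%) | 39 |
| 80% vs 61% | 64.1% (55.6%) | 79.4% (74.6%) | 93.9% (92.1%) | 71 |

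At about 77 per group the pooled-z figures are 11.7%, 97.0% and 83.2% in the same row order.

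The stated 80% can be approached in two ways: 96% vs 77% at 46 per group (Fisher 81.3%), or 80% vs 61% at 69 per group (79.4%). Each needs inputs the protocol does not state.

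**Step 4: smallest gap giving 80% power (pooled z).** With UC fixed at 77%, it is 17.8, 15.2 and 12.2 points at 46, 69 and 115 per group. With CC fixed at 80%, it is 23.9, 19.2 and 14.5 points. None is near 3.

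**Step 5: test-positives only.** The protocol gives no count of positives, so 30 and 23 per group are purely illustrative.

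| PPVs | 30 positives | 23 positives |
|---|---|---|
| 96% vs 77% | 70% (Fisher 55%) | 60% (Fisher 44%) |
| 80% vs 61% | 49% (Fisher 39%) | 41% (Fisher 29%) |

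Pooled z is optimistic at these sizes; the Fisher figures are the safer guide.

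**The case against.** The best defence is that this is a misprint in a draft registry record. The only other PPV in the document is 96%, and 96 − 77 = 19. Five cohorts of 46 make exactly 230, and 96% versus 77% at 46 per group gives 81.3% by Fisher's test. On that reading the design holds and one number needs correcting. The rival pair, 80% versus 61%, comes near 80% power only at 69 or about 77 per group. At 46, the one size that fits five cohorts inside 230, it reaches just 64.1%. A protocol may also leave group sizes to a statistical analysis plan, which is not at hand.

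Much of this stands. A misprint is plausible, inadequate power is not shown, and the missing group sizes are not a separate defect.

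It does not remove the contradiction. The sample-size paragraph never cites the 96%, which came from colectomy specimens, and whether endoscopy biopsies perform alike is what this study is meant to find out. The reading also puts the 92 non-IBD samples inside the 230, while the text speaks of adding them. Finally, 81.3% treats all 46 subjects in each group as test-positive; with fewer positives it falls. A reader cannot safely make the correction on the sponsor's behalf.

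**Conclusion.** The concern holds and must be fixed. The printed PPVs differ by 3 points, not 19, and 80% power does not follow from them under any method or allocation tried. With 80% versus 77%, one-sided power is 9.8% to 13.7% by pooled z (6.1% to 10.5% by Fisher) at 46 to 115 per group. That is some 66 to 70 points below the claim on the pooled-z figures, and it is an upper range because it counts every subject as test-positive.

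That the sentence contradicts itself rests on no assumption. The power figures assume equal groups of the sizes shown. Which number is wrong, and whether 230 is enough, cannot be decided from the protocol.

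**What to change.** Rewrite the sample-size paragraph so that it:

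- gives CC and UC PPVs that differ by the stated amount, with the difference labelled as percentage points;
- gives the number of test-positive CC and UC subjects expected to enter the test;
- says whether the 92 non-IBD samples are part of the 230;
- restates the power for those inputs, naming the test used.

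If 80% versus 77% is truly intended, replace the 80% power with the recomputed value and withdraw the claim that 230 is sufficient. At full group sizes of 46 to 115 that value is at most about 10% to 14%. The 96% versus 77% pair, and any power based on it, should not be adopted unless the sponsor confirms both rates and the test-positive numbers.

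The cost is one corrected paragraph and one recomputation, while the record still reads as not yet recruiting. Whether more specimens are needed can be judged only after that.

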
known IC patients (into authentic UC and CC)
	
because it affects surgical care of patients. Investigators have developed a signature discriminator between UC&CC that also predicts the outcome of IC patients into authentic UC/CC. This is a bioassay that is specific, sensitive, linear, affordable, minimal risk, non-invasive and constitutes an inexpensive, simple to use, point-of-care test format. Our published data have shown robust evidence supporting presence of DEFA5 in the colon crypt mucosa with aberrant expression of apparent crypt-cell-like cells (CCLCs) in areas identified with ectopic colon ileal metaplasia consistent with CC. Investigators propose to validate that UC/CC, the two unsolved medical sub-types of pathology can accurately be distinguished among IC patients by examining CCLCs secreted DEFA5 levels in endoscopy biopsies instantly. Diagnostics relies on the expression/localization/activation of DEFA5 and the ectopic CCLCs in the mucosal crypt of CC patients.

Diverticulitis Correlate patient longitudinal study of clinical data and their biopsy data. Investigators will determine DEFA5 levels from endoscopy biopsies from known diverticulitis.
	
Diagnostic Test: Diagnostic Test The challenge is the discrimination of IBD into the subtypes with accuracy because it affects surgical care of patients. Investigators have developed a signature discriminator between UC&CC that also predicts the outcome of IC patients into authentic UC/CC. This is a bioassay that is specific, sensitive, linear, affordable, minimal risk, non-invasive and constitutes an inexpensive, simple to use, point-of-care test format. Our published data have shown robust evidence supporting presence of DEFA5 in the colon crypt mucosa with aberrant expression of apparent crypt-cell-like cells (CCLCs) in areas identified with ectopic colon ileal metaplasia consistent with CC. Investigators propose to validate that UC/CC, the two unsolved medical sub-types of pathology can accurately be distinguished among IC patients by examining CCLCs secreted DEFA5 levels in endoscopy biopsies instantly. Diagnostics relies on the expression/localization/activation of DEFA5 and the ectopic CCLCs in the mucosal crypt of CC patients.

Groups/Cohorts	Interventions

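### 230 is used both as the size of the two-group CC-versus-UC comparison and as the enrolment of all five cohorts, so the 80% power cannot be tied to any group size

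*Protocol*

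**What the plan says.** The sample-size paragraph (Protocol, Eligibility, Study Population) says "A sample size of 230 subjects is sufficient to detect a clinically significant difference of 19% between the PPVs of CC and UC". The test and error rates behind that claim are given in the same sentence: "using a one-tailed test of proportions between the two groups with 80% statistical power and a 5% level of significance". The paragraph explains the effect as follows: "This 19% difference represents 80% probability that subjects in the CC group with a positive screening test truly have the disease and 77% PPV", the 77% being for UC. It closes with "Investigators will add non-IBD samples, 46 in the DV arm and 46 in CP arm to strengthen the results".

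Study Design records "Enrollment: 230 [Anticipated"] and "Number of Groups/Cohorts: 5". The cohorts listed under Groups and Interventions are CC, UC, IC, diverticulitis and ileum as positive control. The IC cohort is described as "known IC patients (into authentic UC and CC"). No cohort is called CP, and the abbreviation is not defined. No size is given for CC, UC or IC.

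The Brief Summary reports earlier work on colectomy specimens in which DEFA5 was an "independent variable differentiator with a positive predictive value of 96" per cent. The sample-size paragraph does not refer to that figure.

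**The concern.** One number does two jobs. In the sample-size paragraph, 230 supports a test between two groups, with non-IBD samples added. In Study Design, 230 covers five cohorts, two of which are themselves non-IBD. Taken literally, the two statements conflict, and a reader cannot tell whether 230, at most 138, or about 92 specimens bear on the CC-versus-UC contrast.

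The figures meant to support the 80% power do not help to decide. The stated difference is 19 points, but the two PPVs printed differ by 3. The size, the groups it belongs to and the effect are therefore all uncertain in the one passage that justifies the sample size.

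**Working it through.** **Inputs.** From Eligibility, Study Population: N = 230, two groups, one-tailed α = 5%, power 80%, difference 19 points, PPVs 80% (CC) and 77% (UC), and 46 + 46 added samples. From Study Design: enrolment 230, five cohorts. From the Brief Summary: PPV 96%.

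Assumptions, none of them stated in the Protocol:
- CC and UC are equal in size.
- 96% against 77% is one candidate for the intended pair (96 − 77 = 19).
- 80% against 61% is another (61 is 19 points below 80).

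**Step 1: the counts.**
- The 92 on top of 230: 230 + 46 + 46 = 322, before any IC specimens. Enrolment says 230.
- The 92 inside 230: 230 − 92 = 138 for CC, UC and IC together, or 69 per group if all 138 end up in CC or UC in equal numbers.
- Equal cohorts: 5 × 46 = 230, so CC + UC = 2 × 46 = 92.

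**Step 2: can 230 and 80% be reproduced?** With p̄ = (p₁ + p₂)/2, z₀.₉₅ = 1.645 and z₀.₈₀ = 0.842, the size per group is

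n = [1.645·√(2p̄(1 − p̄)) + 0.842·√(p₁(1 − p₁) + p₂(1 − p₂))]² / (p₁ − p₂)².

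For 96% against 77%, p̄ = 0.865 and n = (1.645 × 0.4833 + 0.842 × 0.4642)² / 0.0361 = 38.9, so 39 per group. All pairs:

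| PPV pair | n per group | Total |
|---|---|---|
| 96 vs 77 | 39 (exact Fisher 45) | 78 (90) |
| 80 vs 61 | 71 | 142 |
| 59.5 vs 40.5, the 19-point pair needing most | 85 (95 with continuity correction) | 170 (190) |
| 80 vs 77, as printed | 2,318 | 4,636 |

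None gives 230.

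**Step 3: power at the sizes the text allows.** Power = Φ{[(p₁ − p₂) − 1.645·√(2p̄(1 − p̄)/n)] / √[(p₁(1 − p₁) + p₂(1 − p₂))/n]}. For 96% against 77% at n = 46 this is Φ[(0.19 − 1.645 × 0.0713)/0.0684] = 85.6%.

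| n per group | 96 vs 77 | 80 vs 61 | 80 vs 77 |
|---|---|---|---|
| 46 (five equal cohorts) | 85.6% (Fisher 81.3%) | 64.1% | 9.8% |
| 69 (138 split in two) | 95.4% | 79.4% | 11.2% |
| 115 (230 split in two) | 99.6% | 93.9% | 13.7% |

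At 115 per group, the lowest power over all 19-point pairs is 89.6%.

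**Step 4: denominators.** Steps 2 and 3 count every cohort member. A PPV is computed only among those who test positive, so the effective numbers are smaller. With 115 per group, 80% power would result if 39/115 = 34% (96 vs 77) or 71/115 = 62% (80 vs 61) of each group tested positive. The Protocol states no such share.

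**The case against.** The best defence is that 230 is the whole-study size. DV and CP would be the diverticulitis and ileum cohorts, and the mention of two groups would only describe the test. Then 138 = 3 × 46 is left for CC, UC and IC, and the power fits: one-sided Fisher at 46 per group, 96% against 77%, gives 81.3%, and 45 is the smallest size that reaches 80%. This is the most coherent reading and may well be what was meant. But the Protocol does not say it. On this reading the sentence giving 230 for the CC-versus-UC test is still wrong, because that test has 92 specimens.

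Other points are fair and limit the finding:

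- The text calls 230 sufficient, not minimal, so power above 80% is not in itself a contradiction.
- Unequal groups could bring the power down to about 80%. For example, 46 CC and 184 UC at 80% against 61% gives 80.9%. So could a suitable test-positive share. Neither is stated.
- The 3-point gap is a separate slip. Correcting it alone would leave the conflict over 230 in place.
- Some of the missing detail, such as test-positive denominators, could sit in an analysis plan. The conflict between 230 and the added 92 could not, because it lies in this document.
- The primary outcome is the assessment of two antibodies, not the PPV contrast. The PPV contrast is nevertheless what the Protocol uses to justify its size.

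**Conclusion.** The concern holds. As written, 230 cannot be both the CC plus UC size with 92 further samples and the total over five cohorts. The number bearing on the CC-versus-UC contrast could be 230, at most 138, or about 92. With equal groups, power runs from 9.8% to 99.6% depending on the group size and PPV pair chosen.

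This does not establish underpowering. Two combinations land near the claimed 80%: 46 per group at 96% against 77%, and 69 per group at 80% against 61%. The first assumes that the earlier 96% was the intended CC value. The second assumes a UC value that the text contradicts, and it leaves no separate IC group. All of these figures rest on equal groups and on every member counting towards the PPV. Until the group sizes and a pair that differs by 19 points are stated, the 80% cannot be checked or relied on.

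**What to change.** Rewrite the sample-size paragraph so that it:

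1. gives the size of each cohort, and defines CP by linking it to a listed cohort;
2. says whether the 92 DV and CP samples lie inside the 230;
3. says whether IC specimens resolved to CC or UC count in those groups for this comparison;
4. restates the power from the CC and UC numbers alone, naming the PPV pair used (it must differ by the stated 19 points) and the expected number of test-positives in each group.

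Then make the enrolment figure agree. If 230 really is CC plus UC, enrolment becomes 322 plus any IC specimens, and plus ileum if that is not the CP arm.

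The cost is mainly rewording, and possibly a less favourable stated power. No further specimens are needed if the 92 lie inside 230. If they do not, the recorded enrolment rises by at least 92. Specimens come from an existing repository, with no recruitment specific to this project.
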